#### 7.2.2 Secondary variables

For the secondary variables descriptive statistics will be used to characterize the data; means and 95% confidence intervals will be used for parametric data, medians and interquartile ranges for non-parametric data, and number (proportions) for categorical data. For groups comparisons t-test or ANOVA will be used for parametric distributed data and Wilcoxon, Mann-Whitney or Kruskal-Wallis test will be used for non-parametric distributions respectively, along with post hoc analysis. Categorical data will be compared with Chi-square, McNemar or Sign tests.

Clinical Study Protocol	Unique protocol ID	MISCOS
	Version No:	1.1
	Date:	2025-09-27

Data from the different groups will be compared based on the 'intention to treat' principle. An intention to treat (ITT) analysis means that all patients, regardless of treatment change, loss to follow-up or drop-out, remain in the analysis of the group to which they were randomized. Statistical expertise blinded for treatment allocation will perform the statistical analyses.

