### 6.2 Secondary variables

The secondary variables are listed below.

1. Inpatient stay in days.
2. The deformity correction rate will be assessed as Cobb-angle correction in a postoperative x-ray from the first standing radiograph compared to the last preoperative radiograph. The correction of the curve will be calculated according to the formula:  $(\text{preoperative Cobb angle} - \text{postoperative Cobb angle}) / (\text{preoperative Cobb angle}) \times 100\%$ .
3. Progression of Cobb angle in the operated levels at 2-years standing x-ray compared to the 3-month (first follow-up) x-ray. The progression of the curve will be calculated according to the formula:  $(\text{2-year Cobb angle} - \text{3-month Cobb angle}) / (\text{2-year Cobb angle}) \times 100\%$ .
4. Progression of secondary curve angles at 2-years standing x-ray compared to the 3-month (first follow-up) x-ray. The progression of the curve will be calculated according to the formula:  $(\text{2-year Cobb angle} - \text{3-month Cobb angle}) / (\text{2-year Cobb angle}) \times 100\%$ .
5. Perioperative blood loss (in mL).

Clinical Study Protocol	Unique protocol ID	MISCOS
	Version No:	1.1
	Date:	2025-09-27

6. Total procedure time (from incision to closure) as well as normalized to number of spinal levels from the upper to the lower instrumented vertebra (in min).
7. Accuracy at first attempt: Screws that are not placed and screws that are placed but repositioned after intraoperative verification are noted in the protocol. Accuracy of screw placement will be assessed as a score, calculated as the number of correctly placed screws divided by the total number of screws specified in the protocol (see Appendix 1 in the study protocol). The maximum score is 1, indicating perfect placement according to the preoperative plan. Screws graded Ia or Ib by the Heintel classification [2] are defined as correctly placed. Screws that are not inserted, or that require repositioning after intraoperative verification, will be recorded in the protocol and classified as NOT correctly placed.
8. Intraoperative neurophysiological monitoring. Neurophysiological monitoring is always performed as routine during spinal deformity surgery, with the exception of patients that are non-ambulatory. Motor evoked potential, sensory evoked potential and electromyography data will be collected to investigate any changes in neurophysiological parameters. Any deviations will be noted.

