9. Health economics: Total cost per patient during the first 2 years of the study including cost of possible re-admissions and reoperations related to index surgery. Data on costs on the individual level will be collected. These consist of costs for the inpatient and outpatient visits (including surgery, radiographs, navigation), analgesic and antibiotic treatments as well as possible re-admissions related to index surgery.
10. Patient reported outcome measures. Collected from Swespine or similar platforms after 1, 2, 5 and 10 years.
  - a. SRS-22r: The SRS-22r is a scoliosis specific questionnaire aiming to estimate quality of life in patients with scoliosis [1]. It contains 24 items divided into 5 domains covering function, pain, self-image, mental health, and satisfaction. An index value is calculated for each domain and a total index value is possible to calculate ranging from 1 (worst) to 5 (best).
  - b. EOSQ-24 is a proxy answered questionnaire and will be used in individuals up to the age of 15. It consists of 24 questions of daily function, pain, pulmonary function and mobility [3].
  - c. Oswestry Disability index (ODI) is used in individuals from 15 years and older. ODI is a back specific index measuring disability due to back pain [4]. It is the recommended instrument for studies concerning back pain. An index from 0-100 is calculated. An ODI of 0–20 indicate minimal disability, 21–40; moderate disability, 41–60; severe disability, 61–80; severely crippled, 81–100; bed-bound.
  - d. EQ-5D 3 level is a generic quality of life instrument and consists of five areas reflecting mobility, self-care, usual activities, pain/discomfort and anxiety/depression [5]. Response alternatives range from no problems to extreme problems. An index can be calculated and depending on baseline value set used the index runs between approximately -0.5 (worst possible health) to 1.0 (best possible health). The EQ-5D-3L will be used for health economic analyses. The EQ-VAS is part of the EQ-5D and registers the patient's self-rated health on a visual analogue scale (from 0 to 100; best).

Clinical Study Protocol	Unique protocol ID	MISCOS
	Version No:	1.1
	Date:	2025-09-27

- e. Postoperative pain relief assessed by NRS at discharge. Additionally, given and prescribed doses of analgesics that follow clinical routine protocols will be registered from the hospital files.

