## 7 STATISTICS

### 7.1 Sample size calculation

In order to use the win-odds method for a non-inferiority study we performed more than 1000 simulations using the statistical software R. We used the primary variables listed in 6.1 to calculate our sample size and assumed that the outcomes are independent and that the outcomes were equally distributed among study arms (i.e. we simulated a win-odds of 1.0). We set the power of the study to 80% with a lower limit of confidence interval for win-odds (also called non-inferiority limit) to above 0.60 and calculated a sample size of 150 individuals divided into two treatment arms. We set the possible number of dropouts until the 2-year follow-up to 20%, and the total sample size therefore adjusted to 180 individuals.

**7.1.1** What is a non-inferiority limit. The non-inferiority limit is the probability of a patient in the active arm (minimally invasive procedure) to win over a control patient given an evenly distributed number of ties [6].

**7.1.2** In the case that the MIS group shows slight benefits compared to the open surgery group then the non-inferiority limit will shift towards 1.0 as the win odds will be greater than 1.0 which was assumed in the sample size simulation.

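### If two-year costs are classed as non-parametric, section 7.2.2 gives them medians and a rank test, which do not estimate the difference in mean cost and can favour either arm when mean costs are equal

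*Protocol*

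**What the plan says.** Section 6.2 of the protocol opens its list with "The secondary variables are listed below". Item 9, health economics, is defined as "Total cost per patient during the first 2 years of the study including cost of possible re-admissions and reoperations related to index surgery", and adds that "Data on costs on the individual level will be collected". Section 2.2 gives the same definition among the secondary objectives.

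Section 7.2.2 then sets one rule for the secondary variables. For summaries, "means and 95% confidence intervals will be used for parametric data", and "medians and interquartile ranges for non-parametric data". For comparisons, the parametric branch uses a t-test or ANOVA, and "Wilcoxon, Mann-Whitney or Kruskal-Wallis test will be used for non-parametric distributions". Cost is not exempted, and the section does not say how a variable is to be classified.

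The only other statement on the economic analysis is in item 10d of section 6.2: "The EQ-5D-3L will be used for health economic analyses". It names the utility instrument and gives no estimator for cost.

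**The concern.** A cost comparison normally asks how much more or less one treatment costs in total. The arithmetic mean answers this, because mean cost times number of patients is total cost. Neither a median nor a rank statistic has that property.

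Item 9 deliberately counts re-admissions and reoperations. These fall on a minority of patients and put a long upper tail on the cost distribution. A median hardly responds to that tail. In a Mann-Whitney test a very expensive patient counts only by rank, so a reoperation that doubles the cost and one that multiplies it several times can carry the same weight.

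The two approaches diverge when the arms differ in shape, for instance when one arm has a lower typical cost and a heavier tail. The protocol makes that possible without asserting it: section 1.1 raises a shorter hospital stay with MIS, and reoperation ranks first in a primary endpoint on which non-inferiority is still to be shown. The published cost result could then point away from the actual difference in spending.

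**Working it through.** **Nothing to reproduce.** The protocol gives no mean, SD, difference or power for cost. From the protocol come the definition of cost, the rule in 7.2.2, the 1:1 allocation (5.5) and the sample size. Section 7.1 "calculated a sample size of 150 individuals divided into two treatment arms", so 75 per arm, raised to 180, or 90 per arm. Every cost input below is an assumption. Tests are two-sided at 5%, so the nominal rate in one direction is 2.5%.

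**Step 1: a cheaper index operation with more reoperations.** Assume MIS index cost is 0.95 of open, a reoperation doubles a patient's cost, and 9% (MIS) and 4% (open) are reoperated.

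- Mean cost, open: 1 × (1 + 0.04) = 1.04
- Mean cost, MIS: 0.95 × (1 + 0.09) = 1.0355
- True mean ratio: 1.0355 / 1.04 = 0.996, practically no saving

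At a log-SD of 0.15 the ratio of sample medians averages about 0.96, suggesting a saving of about 4%. The chance that Mann-Whitney significantly favours MIS at 75 per arm depends strongly on the assumed spread of the base cost (lognormal):

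| Log-SD of base cost | Mann-Whitney favours MIS |
|---|---|
| 0.15 | about 26% |
| 0.2 | about 13% |
| 0.3 | about 8% |
| 0.4 to 0.5 | about 4% |

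Repeated simulations differ by one to three percentage points (for example 23% to 26% at 0.15). At 0.15, Welch's t-test favours MIS in about 3.5%. If 12% of MIS patients are reoperated instead, the mean ratio is 0.95 × 1.12 / 1.04 = 1.023. MIS is then 2.3% dearer, yet at a log-SD of 0.15 Mann-Whitney still favours it in about 14% of trials.

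**Step 2: exactly equal means.** Both arms are scaled to a common true mean of 30,000 units, with 2,500 trials per row. Where there are extra-cost events, base mean = 30,000 / (1 + event share × multiple) and the base log-SD is 0.25. For 5% versus 10% at twice the base cost, the base means are 30,000 / 1.10 = 27,273 (open) and 30,000 / 1.20 = 25,000 (MIS).

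| Assumed shape, open v MIS | Favours MIS, 75 / 90 per arm | Favours open, 75 / 90 per arm |
|---|---|---|
| Same shape | 1.8% / 2.1% | 2.7% / 2.8% |
| Events 5% v 8%, each adding 1× base | 5.0% / 5.0% | 1.4% / 1.1% |
| Events 5% v 10%, 1× | 5.8% / 6.6% | 0.9% / 0.6% |
| Events 5% v 15%, 1× | 10.8% / 13.3% | 0.2% / 0.3% |
| Events 5% v 10%, 2× | 23.4% / 27.3% | 0.2% / 0% |
| Log-SD 0.4 v 0.6, no events | 23.0% / 23.8% | 0.2% / 0.1% |
| Log-SD 0.3 v 0.6, no events | 40.1% / 46.2% | 0% / 0% |
| Log-SD 0.6 v 0.3, no events | 0% / 0% | 40.3% / 46.8% |

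In every row Welch's test rejects in 4.6% to 5.9% of trials, both directions together, and the average mean difference is close to zero.

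**Step 3: hand check of one row.** A lognormal median is mean × exp(−SD²/2). At log-SD 0.3 it is 30,000 × exp(−0.045) = 28,680; at 0.6 it is 30,000 × exp(−0.18) = 25,058. The medians differ by about 3,620 units although the means are equal. The simulated difference at 75 and 90 per arm was about 3,560 and 3,600.

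**The case against.** **The protocol does not assign cost to the rank branch.** Section 7.2.2 offers two branches, never mentions skewness and gives no classification test. A reader might infer that the protocol prescribes medians for cost; it does not say so. With 75 to 90 patients per arm an analyst could report mean costs and a t-test within the rule, and the simulations show that this branch behaves well. This stands, and the point is therefore conditional. What remains is that the usual reading of the rule sends a visibly skewed variable to medians, and nothing in the text prevents it for cost.

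**The method may be set elsewhere.** A separate analysis plan or health-economic plan may specify mean costs, and item 10d suggests that an economic analysis is foreseen. Details such as the type of interval belong there. But the protocol does more than leave the matter open: it states a rule for all secondary variables without exempting cost, so a mean-based plan for skewed costs could conflict with it.

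**The distortion needs unequal shapes.** A reader might infer that the rule is tilted towards MIS, or take 26% as the size of the error. The documents support neither. Section 7.1 assumes equally distributed outcomes and section 1.2 hopes for better reoperation results with MIS. With equal shapes the rank test keeps its nominal rate, and with the shapes reversed it favours open surgery. The 26% belongs to a narrow assumed spread and falls close to nominal at wider ones. In that scenario the rank test is also correct on its own terms: typical MIS cost really is 5% lower. It answers a different question.

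**Cost is one of many secondary variables.** It has no stated hypothesis and no bearing on the win-odds conclusion. Patient-level costs are collected, so means can always be computed. This limits the weight of the point without removing it.

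**Conclusion.** The point holds in conditional form. If costs are classed as non-parametric, which is likely but is an inference, the rule in 7.2.2 yields summaries and a test that do not estimate the difference in mean cost, although item 9 is defined to capture the expensive minority that drives it.

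That mismatch does not depend on any assumed figure. Its numerical effect does, and it cannot be fixed from the protocol. Under the scenario with index cost 5% lower, the chance of a significant rank result for MIS is about 4% to 26%, according to spread. With exactly equal means and unequal shapes, the rate for the favoured arm runs from about 5% to 47%, and that arm can be either one. With equal shapes there is no distortion.

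This is a modest but worthwhile correction to a secondary analysis. It does not affect the primary endpoint.

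**What to change.** Add one sentence to section 7.2.2 exempting total cost per patient from the parametric/non-parametric rule. Report the arithmetic mean cost in each arm and the mean difference (MIS minus open) with a bootstrap 95% confidence interval. A gamma generalised linear model with country, the stratification factor in section 3.2, as covariate is an alternative. Medians and interquartile ranges can stay as description. If a separate analysis plan or economic plan exists, it should say the same.

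The change needs no new data and no change to sample size or study procedures. The costs are slightly more analysis work and an interval that may be wider than a rank test would suggest, since uncertainty about the few expensive patients is then shown.

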## 3 STUDY DESIGN AND PROCEDURES

### 3.1 Overall study design and flow chart

This is a multi-center parallel assignment two arm randomized controlled trial (Figure 1). The trial will use a pragmatic approach and use existing equipment and document handling at the participating centers. Data from the existing quality registries for spine surgery will be extracted for outcome assessments.

Randomization between the two treatment arms will take place approximately a week preoperatively, as close to the operation day to minimize selection bias. Postoperative, blinding of the patients and health care personnel will be done.

[figure not shown]
The surgeons will be the only personnel related to patient follow-up that will not be blinded. However, the majority of the analyses, all postoperative imaging and record data collection and analysis will be performed by blinded reviewers.

Patient reported outcomes will be assessed without influence of the care giver.

Clinical Study Protocol	Unique protocol ID	MISCOS
	Version No:	1.1
	Date:	2025-09-27

The Uppsala University hospital performs approximately 80 spine deformity surgeries yearly and it is estimated that  $1/4$  of these meet the inclusion criteria for the study. Similar estimations are done for the rest of the centers with a total enrolment of approximately 50 patients per year. Our time plan includes study start (mid 2025), last patient included (2028) and last 2 year follow up (2029). Registry outcome data are collected preoperatively, at 1 year and 2 years. Registry data may also be collected at 5 and 10 years. The study may have come to an end 2038. However, delays in studies such as these are not uncommon.

Figure 1: Flowchart

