### 3.2 Rationale for study design

We will use a randomized controlled trial design to minimize selection bias and we aim to study advantages and disadvantages of MIS in relation to open approach in scoliosis surgical correction. The study uses a pragmatic approach and uses already available surgical techniques and infrastructures, such as already applicable minimal invasive approaches and existing navigation systems, hospital and quality registries, and picture archiving and communications systems.

Clinical Study Protocol	Unique protocol ID	MISCOS
	Version No:	1.1
	Date:	2025-09-27

Randomization to MIS or open surgery will be done within the Swespine registry-platform or in RedCap. Randomization will be stratified by country. Randomization lists will be prepared in advance by an independent statistician or data manager and will be concealed for the researchers.

Study visits are shown in Table 1. Patients will be assessed before surgery, during surgery and inpatient stay, at 3 months, 2 years and through the Swespine registry at 1, 2, 5 and 10 years. There will also be a 2-4 week surgical wound control by the health care personnel. There will be no additional visits for the patient involved in the study compared to the clinical routine.

**Table 1.** Study activities.

Day:	Visit 1 Screening Initial visit	Visit 2 Inpatient stay/surge- ry	Visit 3 outpatient clinic by Health care personnel 2-4 weeks	Visit 4 3 months	Visit 5 2 years
Informed consent	X				
Demography	X				
Inclusion/exclusion criteria	X				
Randomization		X***			
Surgical wound control			X		
Standing x-rays	X			X	X
2-year low-dose CT and standing x-ray control					X
Outcome assessments	X	X	X*	X**	X**

\*Outcomes related to wound control (SSI)

\*\*Outcomes assessed at regular clinical follow-ups; complications, SSI, readmissions and reoperations. SRS-22r, EOSQ-24, ODI, EQ-5D-5L questionnaires collected as per Swespine routine on web or paper (preop, 1, 2, 5 and 10 year postop).

\*\*\* Randomization will be done approximately a week prior to operation

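### Free gain in precision: Protocol 7.2.2 compares secondary variables without adjustment, although preoperative SRS-22r is collected and randomization is stratified by country

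*Protocol*

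**What the plan says.** Section 7.2.2 gives one general rule for group comparisons of secondary variables: "For groups comparisons t-test or ANOVA will be used for parametric distributed data". Wilcoxon, Mann-Whitney or Kruskal-Wallis tests apply to non-parametric data. It names no baseline covariate and no adjustment for a stratification factor, and no other section of the protocol does.

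Three other statements bear on this rule:

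- SRS-22r is secondary variable 10a in section 6.2, with a total index from 1 to 5. Item 10 says of the patient-reported measures: "Collected from Swespine or similar platforms after 1, 2, 5 and 10 years".
- Section 3.1 says "Registry outcome data are collected preoperatively, at 1 year and 2 years", and the footnote to Table 1 in section 3.2 says "SRS-22r, EOSQ-24, ODI, EQ-5D-5L questionnaires collected as per Swespine routine on web or paper (preop, 1, 2, 5 and 10 year postop". A preoperative SRS-22r is therefore planned for every patient.
- Section 3.2 says "Randomization will be stratified by country".

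**The concern.** When a score is measured before randomized treatment and again afterwards on the same instrument, a two-group test of the follow-up score leaves the variation explained by the preoperative score in the error term. ANCOVA removes it. Two things follow for the 2-year SRS-22r comparison:

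- Its confidence interval is wider than the collected data allow.
- A chance preoperative difference between the arms carries over into the 2-year difference, in proportion to the correlation between the two measurements.

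The country stratification adds a smaller point. If countries differ in outcome and the analysis ignores country, the unadjusted standard error tends to be too large. Putting the stratification factor in the model corrects this.

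What is at stake is the precision of a secondary comparison, not its validity.

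**Working it through.** **There is no stated figure to reproduce.** The protocol gives no SD, expected difference, power or precision for SRS-22r as a secondary variable. Everything below is in SD units of the 2-year score.

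**Inputs from the protocol.** Allocation is 1:1 (section 5.5). Evaluable patients are 150 (section 7.1). Randomized patients are 180 with 20% dropout (section 7.1), which leaves 180 × 0.80 = 144. Confidence intervals are 95% (section 7.2.2).

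**Assumed inputs.** The correlation r between preoperative and 2-year SRS-22r is 0.3 / 0.4 / 0.5. The true difference for the power figures is 0.40 SD, with a two-sided test at 5%.

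**Closed form.** The unadjusted SE is 2/√N. The ANCOVA SE is (2/√N) × √(1 − r²). The half-width is 1.96 × SE. The equivalent unadjusted N is N/(1 − r²).

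- N = 150: SE = 2/√150 = 0.163, half-width 0.320.
- N = 144: SE = 2/√144 = 0.167, half-width 0.327.

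| | unadjusted | r = 0.3 | r = 0.4 | r = 0.5 |
|---|---|---|---|---|
| Variance factor 1 − r² | 1 | 0.91 | 0.84 | 0.75 |
| Half-width, N = 150 | 0.320 | 0.305 | 0.293 | 0.277 |
| Equivalent N for 150 | 150 | 165 | 179 | 200 |
| Half-width, N = 144 | 0.327 | 0.312 | 0.299 | 0.283 |
| Equivalent N for 144 | 144 | 158 | 171 | 192 |

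**Carry-over of chance imbalance.** The shift is r × the baseline imbalance. For an imbalance of one standard error at N = 144 (0.167 SD), the unadjusted 2-year difference moves by 0.050 / 0.067 / 0.083 SD.

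**Simulation with less ideal conditions.** Settings were 6,000 trials each, 144 patients, three assumed countries (60/25/15%), arms balanced within country, and country shifts of 0 or ±0.3 SD. Either 0 or 10% of baselines were missing and replaced by the mean over both arms.

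| | r = 0 | r = 0.3 | r = 0.4 | r = 0.5 |
|---|---|---|---|---|
| Variance ratio, ANCOVA to t-test | 1.004-1.006 | 0.916-0.935 | 0.850-0.871 | 0.752-0.802 |
| ANCOVA power for 0.40 SD | not quoted | 0.695-0.710 | 0.718-0.736 | 0.768-0.781 |

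The t-test had power 0.642-0.675. Two-sided type I error was 4.4-5.4% for the t-test and 4.5-5.6% for ANCOVA, so both hold their level. A separate simulation of 3,000 trials per setting gave variance ratios of 0.91-0.94, 0.85-0.87 and 0.75-0.78, and 1.004-1.009 at r = 0.

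Closed-form power at N = 144 would be 71 / 75 / 79%. These values lie at or above the top of the simulated ranges, so the simulated ranges are the ones to rely on.

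**The case against.** **The rule is a generic menu, and no error is shown.** Section 7.2.2 names neither SRS-22r nor the 2-year time point. It includes paired tests, and it does not say whether scores or changes are compared. Covariates for single secondary outcomes are often settled in the SAP. All this is fair and keeps the point minor. It does not remove it: a method is stated, and an SAP that used ANCOVA would depart from 7.2.2 as written. Reading the rule as a t-test on change scores does not help. With equal SDs at both times the variance factor would be 2(1 − r) = 1.4 / 1.2 / 1.0, against 0.91 / 0.84 / 0.75 for ANCOVA.

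**The size rests on assumptions.** This stands. At r = 0.3 the gain is small. If the 1-to-5 index is treated as non-parametric, 7.2.2 sends it to a rank test, and these gains do not carry over directly.

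**Stronger readings that a reader might infer.**

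- *That the secondary results would be biased or invalid.* Randomization makes the unadjusted comparison valid, and its type I error is held.
- *That the primary analysis needs the same adjustment, since SRS-22r is also its sixth level.* Section 7.2.2 does not govern the win odds. A second, adjusted non-inferiority result would also need a rule for disagreement between the two.
- *That item 10 of section 6.2 contradicts preoperative collection.* It lists follow-up times; sections 3.1 and 3.2 both state the preoperative measurement.
- *That every patient-reported score should be adjusted, or that none but SRS-22r can be.* Neither holds. "EOSQ-24 is a proxy answered questionnaire and will be used in individuals up to the age of 15", whereas "Oswestry Disability index (ODI) is used in individuals from 15 years and older". A patient who passes that age during follow-up changes instrument, but one aged 15 or older at surgery has ODI at both times.

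**Conclusion.** The point holds as a free improvement in precision for a secondary comparison.

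Under an assumed correlation of 0.3 / 0.4 / 0.5, variance falls by 9% / 16% / 25% in closed form and by about 6-8% / 13-15% / 20-25% with country terms and 0-10% missing baselines. At 144 evaluable, simulated power for an assumed 0.40 SD difference rises from about 64-68% to about 70-71% / 72-74% / 77-78%.

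The direction does not depend on the exact correlation: there was a gain at every non-zero value examined. The size does depend on it, and the protocol gives no value. The gain from country alone cannot be quantified from the document, because it gives no between-country differences.

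**What to change.** In section 7.2.2, add that 2-year SRS-22r is compared by ANCOVA with preoperative SRS-22r and country as covariates, reported as the adjusted difference with its 95% CI. State also:

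- a pre-specified rule for pooling small countries;
- that a missing preoperative value is replaced by the mean over both arms, so that no patient is lost from the intention-to-treat comparison for that reason;
- that the rank test is kept as a sensitivity analysis.

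The same model may be used for any other score with a preoperative value on the same instrument, for example ODI in patients aged 15 or older at surgery. Outcomes without a baseline (inpatient stay, blood loss, procedure time, screw accuracy) keep the stated tests. Section 7.2.1 stays as it is.

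The cost is a few sentences and a little programming, with no new data or visits. If the preoperative score turns out not to be prognostic, the price is about 0.5-1% more variance.

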## **2.2 Secondary objectives**

The following secondary objectives will be studied in comparisons between MIS and open operating procedures.

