## 5.5 Randomization

The subjects are randomized in a 1:1 ratio, for MIS or open technique treatment arms. Randomization will be performed through the web-based platform of the Swespine registry (or similar platforms like RedCap) using an allocation sequence hidden from the healthcare personnel and provided independent from the study. Block randomization will be used. Block sizes will be unknown for the researchers. The inclusion will end when the sample size has been reached in both intervention arms.

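### Section 7.2.2 offers paired McNemar and Sign tests although the only stated comparison is between independent arms, and it leaves preoperative PROM values unused

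*Protocol*

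**What the plan says.** Protocol section 7.2.2 sets the analysis of the secondary variables. It summarises by type of data, with "medians and interquartile ranges for non-parametric data, and number (proportions) for categorical data". It then turns to comparing groups: "For groups comparisons t-test or ANOVA will be used for parametric distributed data", with Wilcoxon, Mann-Whitney or Kruskal-Wallis for non-parametric data, and post hoc analysis. The next sentence reads: "Categorical data will be compared with Chi-square, McNemar or Sign tests". No rule says which of the three tests serves which comparison.

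Section 2.2 gives the purpose of these analyses: "The following secondary objectives will be studied in comparisons between MIS and open operating procedures". Section 3.1 describes a parallel two-arm design, and section 5.5 says: "The subjects are randomized in a 1:1 ratio, for MIS or open technique treatment arms". Randomisation is in blocks (5.5) and stratified by country (3.2). Nowhere are patients matched.

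On PROMs, section 6.2 item 10 says: "Collected from Swespine or similar platforms after 1, 2, 5 and 10 years". Section 3.1 and the footnote to Table 1 in section 3.2 add a preoperative collection. Section 6.2 uses ODI from age 15 upward and EOSQ-24 up to 15; enrolment starts at age 10 (4.1).

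**The concern.** McNemar and Sign tests work on differences within pairs: the same patient twice, or two patients matched by design. A MIS patient and an open-surgery patient in this trial form no pair. The sentence on categorical data follows directly on the one about comparing groups, and the next paragraph concerns comparing the groups by intention to treat. The natural reading is therefore that all three tests are on offer for MIS versus open. An analyst who took up a paired test would have to invent a pairing, and different pairings of the same data can fall on either side of 0.05. With unequal arms after dropout, some patients would also have no partner and would be lost.

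The second matter is efficiency. A t-test or rank test that ignores the preoperative score leaves unused information that the trial already collects, on outcomes that tend to correlate with their own baseline. Here no error is made; precision is given away.

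**Working it through.** The protocol states no figure on this point, so there is none to reproduce.

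**1. Does any stated comparison have pairs?**
- Section 2.2: the comparisons are between MIS and open.
- Sections 3.1 and 5.5: parallel arms, individual 1:1 allocation in blocks, no matching.
- Section 6.2: repeated measurements exist (PROMs over the years, radiographs at 3 months and 2 years), so within-patient comparisons are possible. No within-patient test of a categorical outcome is stated.
- The plainest categorical item outside the PROMs is neuromonitoring deviations (6.2 item 8). It is recorded during surgery and has no before-and-after pair.

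The two paired tests therefore fit no comparison that the protocol states.

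**2. What would a paired test do between arms?** Inputs: 75 per arm, from section 7.1 ("calculated a sample size of 150 individuals divided into two treatment arms"), and *assumed* event counts of 8 and 19, which are not from the protocol.
- Proportions: 8/75 = 0.107 and 19/75 = 0.253; difference 0.147.
- Chi-square (uncorrected): pooled proportion 27/150 = 0.18; z = 0.1467 / √(0.18 × 0.82 × 2/75) = 2.34; z² = 5.47; p = 0.019. This does not depend on the order of the patients.
- Risk difference, Wald 95% CI: SE = √(0.107 × 0.893/75 + 0.253 × 0.747/75) = 0.0616; 0.147 ± 1.96 × 0.0616 = 0.026 to 0.267.
- Exact McNemar (the same as a sign test on discordant pairs): if *k* pairs happen to join two patients with events, the discordant counts are 8 − *k* and 19 − *k*.

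| *k* | discordant pairs | exact p |
|---|---|---|
| 0 | 8 vs 19 | 0.052 |
| 2 | 6 vs 17 | 0.035 |
| 4 | 4 vs 15 | 0.019 |
| 7 | 1 vs 12 | 0.003 |

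Over 5,000 random pairings p ran from 0.003 to 0.052. The data never change, only the arbitrary *k*.

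**3. Is the type I error lost?** With equal arms and a pairing made without regard to outcome, the two discordant cells have equal probability under the null. In simulations with 75 per arm, 20,000 runs and assumed event rates of 5%, 10%, 20% and 50%, exact McNemar rejected in about 2% to 3.5% of runs and asymptotic McNemar in about 4% to 5%, at a nominal 5%. The error rate is kept; what is lost is a unique answer.

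**4. What would baseline adjustment gain?** With pre-post correlation *r* (assumed; the protocol gives none), ANCOVA reduces the variance of the arm difference, compared with an unadjusted comparison of follow-up scores, by about *r*². The equivalent gain in sample size is 1/(1 − *r*²).

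| *r* | variance reduction | equivalent sample size |
|---|---|---|
| 0.3 | 9% | × 1.10 |
| 0.5 | 25% | × 1.33 |
| 0.6 | 36% | × 1.56 |

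**5. Where are baselines available?** SRS-22r and EQ-5D are collected preoperatively with no stated age limit. ODI is not: a patient operated on at 13 has ODI at 2 years but no preoperative ODI.

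**The case against.** The sentence on categorical data does not itself say that it concerns the arms, and section 7.2.2 is a generic list. EQ-5D levels and ODI bands are categorical and repeated in the same patient, so McNemar or Sign could have been meant for change over time. That is possible, and it is why restricting the tests is as good a remedy as deleting them. It does not remove the point, since no such within-patient comparison is stated and section 2.2 names only MIS versus open.

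The scope is small. Most secondary variables are numeric (stay, correction, progression, blood loss, time, screw score, cost), Chi-square is available for the rest, and the primary win-odds analysis in 7.2.1 is untouched. All of this stands.

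A reader might infer that the plan yields no valid effect estimate for categorical outcomes. It does not follow: Chi-square is the first test listed and is valid for independent arms, and the planned proportions give a risk difference directly. An effect measure and interval method not named here may well be in a statistical analysis plan. A reader might also infer that the paired tests have no valid error rate; step 3 of the working shows otherwise for a pairing blind to outcome. Nor are ANOVA and Kruskal-Wallis wrong with two arms: they reduce to the equal-variance t-test and the Mann-Whitney test, and post hoc tests have nothing left to separate.

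On ANCOVA, the fair reply is that an unadjusted comparison of randomised arms is unbiased, that the gain rests on an assumed correlation, and that adjustment is often settled in the analysis plan. This part is therefore an inexpensive improvement, not a correction of an error. Section 7.2.2 also does not say whether follow-up scores or changes are compared; the gains above are relative to follow-up scores.

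**Conclusion.** The point holds, and it is minor. Two of the three tests named for categorical secondary data do not fit the only comparison the protocol states, and used between arms they would give an answer that depends on an arbitrary pairing (p from 0.003 to 0.052 on one assumed set of counts, against a single Chi-square p of 0.019). Since Chi-square is listed beside them, the plan already contains a valid analysis; what it lacks is a restriction on the other two.

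Separately, the secondary PROM comparisons could be made more precise at almost no cost: about 9% to 36% less variance for pre-post correlations of 0.3 to 0.6, which are assumptions. This applies cleanly to SRS-22r and EQ-5D, and to ODI only in patients who have a preoperative score.

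**What to change.** In section 7.2.2:

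- Delete McNemar and Sign tests, or state that they serve only within-patient change. For MIS versus open, keep Chi-square, with an exact test where counts are sparse.
- ANOVA, Kruskal-Wallis and post hoc analysis may be dropped for the two-arm comparison, for tidiness.
- For SRS-22r and EQ-5D as secondary outcomes, compare the arms by ANCOVA with the preoperative value and country as covariates; country is already a stratification factor.
- For ODI, use the same model only where a preoperative ODI exists, and say that patients under 15 at surgery will not have one.

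The cost is a change of wording before the database is locked. No new data, visits or patients are needed, because the preoperative SRS-22r and EQ-5D are already collected. The primary analysis and the sample size do not change.
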